## ABSTRACT

Third molar extraction is a common oral surgical procedure often associated with postoperative pain, edema, and functional limitation. Effective postoperative management plays a key role in minimizing morbidity and promoting patient comfort. Strategies such as cryotherapy may contribute to improved recovery and quality of life after surgery. **Objective:** to investigate the effects of cryotherapy on postoperative outcomes (pain intensity, edema, trismus and quality of life) following mandibular third molar extraction. **Materials and Methods:** This study was designed as a randomized split-mouth clinical trial. The sample consisted of 17 patients (34 mandibular third molars with equivalent levels of impaction) who underwent bilateral surgical extraction. The surgical sites were allocated into two groups according to postoperative care: Group A (control side—without cryotherapy) and Group B (test side—with postoperative cryotherapy using ice packs). All intraoperative and postoperative procedures, instructions, and medications were identical for both groups. Patients were evaluated for pain intensity, trismus severity, presence of edema, and quality of life for up to seven days postoperatively (D7). The evaluator was aware of the postoperative intervention applied. Repeated-measures ANOVA was used to analyze each outcome variable, and associations between continuous variables were assessed using Pearson's correlation test. Statistical significance was set at 5% ( $P < 0.05$ ). **Results:** Overall, postoperative pain intensity was lower in patients who received cryotherapy. Group A reported significantly higher pain intensity on postoperative days 1 and 3. No signs of trismus were observed in Group B at the end of the follow-up period, whereas Group A presented restricted mouth opening at D7. Both groups exhibited edema on postoperative day 2 (D2); however, complete regression of edema by D7 was observed only in Group B. Additionally, a significant association between pain intensity and trismus severity was identified in Group A at D7. Quality-of-life assessment revealed significant differences in three questionnaire items favoring Group B, including greater perceived improvement, better mouth opening, and reduced difficulty sleeping. **Conclusion:** The findings suggest that postoperative cryotherapy is effective in reducing pain intensity and trismus following mandibular third molar extraction. Moreover, this physical therapy modality appears to enhance pain tolerance and patients' self-perceived healing.

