#### **4.4 SAMPLE**

The sample selection consisted on patients referred to the Federal University of Rio Grande do Sul's Dentistry School. The selected patients require bilateral extraction of lower third molars under local anesthesia in two different surgical times. There will be no change to the routine care for patients volunteering in the study. The surgical procedures will be performed by the research team responsible for this study. Participants of both sexes, aged 18 to 50 years, were included in the study if they presented an indication for bilateral surgical removal of mandibular third molars in similar positions according to Pell and Gregory classification. Additional inclusion criteria comprised the absence of systemic comorbidities, local conditions free of inflammatory or infectious processes, no history of allergy to the prescribed medications, and no recent or chronic use of antibiotics, anti-inflammatory drugs, corticosteroids, or analgesics. Participants were excluded from the study if they used medications other than those prescribed by the surgeon, failed to provide the required data, belonged to Group A (control) but used postoperative ice packs, or belonged to Group B (test) and did not use ice packs as instructed by the researchers. There were three dropouts due to noncompliance with postoperative recommendations and the use of non-prescribed medication, resulting in 34 procedures performed in 17 patients.

Postoperative consultations were conducted for follow-up, suture removal, and the evaluation and treatment of any potential postoperative complications.

The selection of the control group and experimental groups were determined by a simple randomization in the immediate postoperative period. One surgical site didn't receive cryotherapy (GA), while the other site received cryotherapy with ice (GB).

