#### 4.8 STATISTICAL ANALYSIS

Data normality was assessed using the Kolmogorov–Smirnov test. Parametric analyses were applied to compare groups (control side vs. test side) and postoperative time points (from day 0 to day 7). Continuous variables, including pain intensity (VAS scores), maximum mouth opening (mm), and facial edema (mm), were expressed as means  $\pm$  standard deviation (SD).

A two-way repeated-measures analysis of variance (ANOVA), followed by Fisher's least significant difference (LSD) post hoc test, was used to evaluate the main effects of time and treatment, as well as their interaction, for pain intensity, trismus, and edema. Pain reports were also qualitatively analyzed based on the frequency distribution of pain categories (no pain, mild pain, moderate pain, and severe pain) for both groups.

Associations between pain intensity and trismus or edema were assessed using Pearson's correlation coefficient. Trismus and edema were additionally evaluated using the formulas (Baseline – Postoperative) and (Postoperative – Baseline), respectively. Qualitative data related to quality of life were presented as percentages.

All statistical analyses were performed using SPSS software (version 20.0; IBM Corp., Armonk, NY, USA). Statistical significance was set at  $P < 0.05$ .

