## 5.2 TRISMUS

Cryotherapy did not significantly affect maximum mouth opening during the postoperative period ( $F_{(1,16)} = 0.006$ ,  $p = 0.93$ ). However, a significant effect of time ( $F_{(2,32)} = 45.410$ ,  $p < 0.001$ ) and a significant interaction between treatment and time ( $F_{(2,32)} = 4.703$ ,  $p = 0.016$ ) were observed.

Mouth opening decreased on postoperative day 2 compared with baseline in both the control group ( $43.8 \pm 8.9$  vs.  $30.1 \pm 12.2$ ;  $p < 0.001$ ) and the cryotherapy group ( $39.3 \pm 8.8$  vs.  $31.4 \pm 7.9$ ;  $p < 0.01$ ). In Group A, mouth opening remained significantly reduced on postoperative day 7 compared with baseline ( $43.8 \pm 8.9$  vs.  $37.8 \pm 13.6$ ;  $p = 0.005$ ). In contrast, Group B showed recovery of mouth opening by day 7, with values comparable to baseline ( $39.3 \pm 8.8$  vs.  $40.5 \pm 8.5$ ;  $p = 0.43$ ) (Table 2).

[figure not shown]

Table 2: Average of maximal mouth opening values on days 0, 2 and 7 post-op.

Correlation analysis revealed no significant association between pain intensity

and trismus in Group B on postoperative days 2 ( $r = 0.15$ ,  $p = 0.54$ ) or 7 ( $r = 0.11$ ,  $p = 0.66$ ). In contrast, a significant positive correlation was observed in Group A on postoperative day 7 ( $r = 0.62$ ,  $p = 0.005$ ), indicating that greater pain intensity was associated with increased mouth opening restriction. No correlation was found on postoperative day 2 in Group A ( $r = 0.30$ ,  $p = 0.23$ ) (Table 3).

[figure not shown]

Table 3: Correlation between pain and trismus for control group.

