A strong association was also observed between higher pain intensity reports and increased requests for rescue medication in the control group. These results indicate that failure to use cryotherapy may increase reliance on pharmacological interventions to manage postoperative discomfort, which could otherwise be mitigated through a simple and low-cost intervention such as ice pack application for 30 minutes over a 12-hour period. Therefore, the proposed cryotherapy protocol can be considered a safe and effective approach that enhances postoperative predictability, facilitates complication control, and promotes greater patient engagement in self-care.

Trismus represents a multifactorial postoperative response influenced by surgical trauma, including osteotomy, extracellular fluid extravasation, tissue hemorrhage, and muscle fiber incision. Given the simultaneous occurrence of these factors, significant benefits of cryotherapy are not expected before consolidation of the inflammatory response, which explains the absence of intergroup differences during the first 72 postoperative hours. However, when comparing immediate postoperative measurements with those obtained on postoperative day 7, the control

group exhibited significantly greater mouth opening limitation (Table 2), indicating a longer duration of trismus. This finding is supported by the statistically significant correlation between pain intensity and trismus observed exclusively in the control group (Table 3), suggesting that higher pain levels are associated with prolonged mouth opening restriction. These results were further corroborated by the quality-of-life questionnaire, which revealed greater difficulty in mouth opening among control participants.

Edema did not show statistically significant differences between groups (Table 4), consistent with previous reports. It is hypothesized that superficial ice application may be insufficient to significantly reduce edema due to its limited penetration into deeper muscular and facial tissue planes, thereby restricting its vasoconstrictive effects.

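### Two of the four pain–trismus correlation p-values do not reproduce with 17 patients, and the control-side correlation is used as support for longer trismus without any comparison of the two sides

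*Combined protocol and SAP*

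**What the plan says.** Section 4.4 reports three dropouts, "resulting in 34 procedures performed in 17 patients". The degrees of freedom in section 5.2, F(1,16) and F(2,32), agree with 17 patients.

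On method, section 4.8 says: "Associations between pain intensity and trismus or edema were assessed using" Pearson's coefficient. It plans no comparison of the two sides' correlations.

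Section 5.2 states that "a significant positive correlation was observed in Group A on postoperative day 7" and prints four pain–trismus correlations:

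| Side, day | r | p |
|---|---|---|
| Group A (control), day 2 | 0.30 | 0.23 |
| Group A (control), day 7 | 0.62 | 0.005 |
| Group B (cryotherapy), day 2 | 0.15 | 0.54 |
| Group B (cryotherapy), day 7 | 0.11 | 0.66 |

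No n is given in the text for any of them. Table 3, the correlation table for the control group, is a figure not shown.

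The Discussion (section 6) says that trismus lasted longer in the control group and offers as support the "statistically significant correlation between pain intensity and trismus observed exclusively in the control group".

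**The concern.** With Pearson's test, r and n fix p. If p does not follow from r and the stated n, then the n, the degrees of freedom, the r or the p is wrong. One of the affected values is the only significant one of the four, and the one on which the Discussion relies.

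The second issue is the inference. Significance on one side and not on the other does not show that the two correlations differ. A correlation within the control side says that patients with more pain had more restricted opening. It does not say that restriction lasted longer on that side than on the other. This matters because the treatment main effect on mouth opening was null (F = 0.006, p = 0.93), so the trismus claim depends on how the time course is argued.

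**Working it through.** **Inputs.** n = 17 (section 4.4, confirmed by the ANOVA degrees of freedom); r and p as printed in section 5.2. The documents do not state whether tests are one- or two-sided, so two-sided is assumed and one-sided is tried as a variant.

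**Formula.** t = r·√(n − 2) / √(1 − r²), on n − 2 = 15 df. Each r is also varied over its rounding interval of ±0.005.

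**Group A, day 7.** t = 0.62 × √15 / √(1 − 0.3844) = 3.06, so p = 0.0079.

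| Side, day | r | Printed p | p at n = 17 | Range over rounding of r | Fits n = 17? |
|---|---|---|---|---|---|
| A, day 2 | 0.30 | 0.23 | 0.242 | 0.234–0.250 | only at the edge |
| A, day 7 | 0.62 | 0.005 | 0.0079 | 0.0073–0.0086 | no |
| B, day 2 | 0.15 | 0.54 | 0.566 | 0.553–0.579 | no |
| B, day 7 | 0.11 | 0.66 | 0.674 | 0.660–0.688 | only at the edge |

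At the printed r, all four printed p-values are smaller than n = 17 gives.

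**Variants for Group A, day 7 at n = 17.** The one-sided p is 0.0040 and the Fisher z version gives 0.0067. Neither is 0.005. The other printed values are clearly not one-sided: Group A day 2 would be 0.121.

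**Other sample sizes.** With n = 18 (16 df) the ranges over the rounding of r are:
- A, day 2: 0.218–0.235 (fits 0.23)
- A, day 7: 0.00555–0.0066 (a value that rounds to 0.005 must be below 0.0055, so it misses by 0.00005)
- B, day 2: 0.539–0.566 (fits 0.54)
- B, day 7: 0.650–0.678 (fits 0.66)

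If p was truncated instead of rounded, n = 18 fits all four. Under ordinary rounding, Group A day 7 fits only n = 19 (p = 0.0046 at r = 0.62), while Group A day 2 fits only n = 17 or 18.

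**Comparison of the day 7 correlations.** None is reported. Treating the sides as independent, which they are not, the Fisher z difference is (0.725 − 0.110) / √(1/14 + 1/14) = 0.6146 / 0.378 = 1.63, p = 0.10. Both correlations come from the same 17 patients, so the correct test also needs the cross-side correlations, which the documents do not give. With assumed values in a test for dependent correlations:

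| Assumed correlation of the same variable across sides | Assumed other cross-side correlations | p for the difference |
|---|---|---|
| 0 | 0 | 0.10 |
| 0.5 | 0 to 0.3 | 0.03–0.06 |
| 0.8 | 0.3 | 0.003 |

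The answer therefore runs from non-significant to clearly significant, depending on figures that are not available.

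**The case against.** The strongest reply is that this is a small reporting slip in an ancillary analysis. Much of that stands.

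- The corrected p of 0.008 is still below 0.05, and Bonferroni over the four tests gives 4 × 0.0079 = 0.03. The three non-significant results stay non-significant. A reader might infer that the finding is lost; it is not.
- A reader might infer that different data sets were used, or that the excluded patients entered the correlations. The documents do not support this. Using 18 in place of 17, or equivalently 16 df in place of 15, misses fitting all four values by only 0.00005 and fits them all under truncation. Nothing says that dropouts were included, and an n printed in Table 3 could not be checked.
- A reader might take p = 0.10, or the overlap of the day 7 confidence intervals (0.20 to 0.85 for Group A, −0.39 to 0.56 for Group B, at n = 17), as evidence that the correlations do not differ. Neither is valid for paired sides. One can say only that the difference was not tested.
- The word *exclusively* is literally accurate as a description of where significance was found, and all four results are openly printed.
- The trismus argument rests first on the treatment-by-time interaction (p = 0.016) and the within-side day 7 comparisons. The Conclusion does not cite the correlation, and the Abstract reports it only as an association in Group A.

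What the reply does not remove is that two printed p-values cannot come from the stated sample, and that the Discussion uses the control-side result to support a statement about the difference between sides.

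**Conclusion.** The point holds in a limited form. Two of the four p-values are incompatible with 17 patients beyond rounding: 0.008 against the printed 0.005, and 0.57 against the printed 0.54. This assumes two-sided Pearson tests on complete data for 17 patients. The cause is unknown; a one-unit slip in n or df would nearly explain all four. No significance statement changes.

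The use made of the correlation in the Discussion is not supported. The sides were not compared, whether they differ cannot be determined from the documents, and even a correct r = 0.62 within the control side would not show longer trismus there. The main trismus results are untouched by this point. It is a correction that should be made, of modest weight.

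**What to change.** 1. Re-run the four correlations on the 17 analysed patients. Print n, r, 95% CI and p for each in section 5.2 and Table 3. If any correlation used a different number of patients, state it and say why.
2. Either compare the two day 7 correlations with a method for paired data (a test for dependent correlations, or a bootstrap that resamples patients with both sides together), or drop the between-side inference.
3. In section 6, remove the clause that presents the correlation as support for longer trismus in the control group. A comparison under item 2 would not restore it, because a correlation does not measure duration.
4. Label the pain–trismus correlations exploratory in sections 4.8 and 5.2.

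The cost is four re-run correlations, at most one additional test, and some edited text. The Group A day 7 p-value becomes slightly less favourable, and the Discussion loses one supporting sentence.

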### 5.3 EDEMA

Time significantly affected postoperative edema ( $F_{(2,32)} = 10.34$ ,  $p < 0.001$ ), whereas treatment ( $F_{(1,16)} = 0.516$ ,  $p = 0.48$ ) and the interaction between factors ( $F_{(2,32)} = 1.533$ ,  $p = 0.23$ ) did not.

Both groups exhibited greater edema on postoperative day 2 compared with baseline (Group A:  $123.0 \pm 5.1$  vs.  $126.2 \pm 7.8$ ,  $p = 0.02$ ; Group B:  $123.1 \pm 7.1$  vs.  $126.3 \pm 7.5$ ,  $p = 0.005$ ). No significant differences were observed between baseline and postoperative day 7 in either Group A ( $123.0 \pm 5.1$  vs.  $126.1 \pm 7.8$ ;  $p = 0.86$ ) or Group B ( $123.1 \pm 7.1$  vs.  $123.5 \pm 8.7$ ;  $p = 0.71$ ), indicating resolution of edema by the end of the evaluation period in both groups (Table 4).

[figure not shown]

Table 4: Average of edema values on days 0, 2 and 7 post-op.

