## 7 CONCLUSION

Postoperative cryotherapy was effective in reducing pain intensity and duration, decreasing the need for rescue medication, and shortening the period of mouth opening limitation after mandibular third molar extraction. This intervention also improved patients' perception of recovery and contributed to a more predictable postoperative course. However, cryotherapy did not demonstrate a significant effect on postoperative edema.

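### The Group A day-7 edema p = 0.86 in 5.3 cannot come from its printed means and SDs, and 5.3 and the Abstract contradict each other on whether Group A edema resolved

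*Combined protocol and SAP*

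**What the plan says.** Section 4.8 specifies a two-way repeated-measures ANOVA with Fisher's "least significant difference (LSD) post hoc test" for pain, trismus and edema. It declares that ± means SD for all three.

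Section 5.3 states "Time significantly affected postoperative edema" (F = 10.34), with no effect of treatment (F = 0.516, p = 0.48) or of the interaction (F = 1.533, p = 0.23). For day 2 it says "Both groups exhibited greater edema on postoperative day 2 compared with baseline": Group A 123.0 ± 5.1 to 126.2 ± 7.8, p = 0.02; Group B 123.1 ± 7.1 to 126.3 ± 7.5, p = 0.005. For day 7 it says "No significant differences were observed between baseline and postoperative day 7 in either Group A" (126.1 ± 7.8, p = 0.86) or Group B (123.5 ± 8.7, p = 0.71), "indicating resolution of edema by the end of the evaluation period in both groups".

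The Abstract says "complete regression of edema by D7 was observed only in Group B". The Discussion says "Edema did not show statistically significant differences between groups" and the Conclusion says "cryotherapy did not demonstrate a significant effect on postoperative edema". Neither addresses recovery within Group A.

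Section 5.1 prints daily pain values with ± between 0.33 and 0.59, and overall values of 2.0 ± 1.2 and 1.3 ± 1.1.

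**The concern.** The inconsistency in 5.3 shows before any calculation. In Group A, a 3.2 mm difference has p = 0.02 on day 2, and a 3.1 mm difference with the same SDs has p = 0.86 on day 7.

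That p-value is the only support for saying that Group A edema resolved. The Abstract's opposite statement agrees with the printed mean. A reader cannot tell whether control-side edema had gone by day 7. Someone who reads only the Abstract sees the two groups' recovery set against each other without the between-group null result, and may infer an edema benefit that the Conclusion denies.

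The pain issue is one of labelling. Anyone who takes the daily ± values as SDs, for a meta-analysis for example, would understate the spread by a factor of √17, about 4.1.

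**Working it through.** **Inputs.** There are 17 complete pairs (section 4.4; the error degrees of freedom 16 and 32 agree). Means, SDs, p-values and F values are from 5.1 and 5.3. Tests are taken as two-sided. Contrasts are taken as paired within group, because equal rises of 3.2 mm carry different p-values (0.02 and 0.005), which a single pooled error would not give.

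**What reproduces.** F(1,16) = 0.516 gives p = 0.483, and F(2,32) = 1.533 gives p = 0.231, as printed. For each contrast, paired SD = difference × √17 / t, with t on 16 df from the printed p. The implied correlation is (s1² + s2² − SD²) / (2·s1·s2).

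| Contrast | Difference (mm) | Printed p | Paired SD needed | Implied correlation |
|---|---|---|---|---|
| A, day 2 | 3.2 | 0.02 | 5.11 | 0.76 |
| B, day 2 | 3.2 | 0.005 | 4.06 | 0.85 |
| B, day 7 | 0.4 | 0.71 | 4.36 | 0.87 |
| A, day 7 | 3.1 | 0.86 | 71 | none possible |

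**The bound for A, day 7.** The paired SD cannot exceed s1 + s2 = 5.1 + 7.8 = 12.9. So t ≥ 3.1 / (12.9/4.123) = 0.991 and p ≤ 0.337. With worst-case rounding, 3.0 / (13.0/4.123) = 0.951 and p ≤ 0.356. An unpaired test gives 0.18. At correlation 0.76 the paired SD is 5.14 and p = 0.024; at 0.87 it is 4.20 and p = 0.008. p falls below 0.05 once the correlation exceeds about 0.63.

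**Which entry is more likely wrong.**

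- The printed means with 126.1 give mean squares of 87.3 (time) and 20.7 (interaction). Dividing by the printed F values gives error mean squares of 87.3/10.34 = 8.44 and 20.7/1.533 = 13.5, which are feasible.
- With the day-7 mean moved near baseline, the interaction error falls to 0.30 (mean 123.0) or 0.07 (mean 123.2).
- The two error mean squares sum to one sixth of the total of the six within-group pairwise difference variances. With 126.1 that total is 6 × (8.44 + 13.47) = 131.5. Subtracting 26.1, 16.5 and 19.0 for the three attainable contrasts leaves 70.0 for the other three. The triangle inequality on SDs then caps the A baseline-to-day-7 SD at about 7.9, so p is at most about 0.125 (0.16 with rounding).
- With 123.0 only about 3.6 is left, while the two remaining Group A terms alone need at least 26.1/2 = 13.0.

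**Explanations that fit the other printed edema values.** One is a decimal slip, p = 0.086 (paired SD 7.0, correlation 0.48). Another is a mislabelled day-2-versus-day-7 contrast (0.1 mm, paired SD 2.3), in which case the true baseline-versus-day-7 p lies between 0.0003 and 0.104. Group B's p = 0.71 does fit its label: as day 2 versus day 7 it would need an SD of 2.8 × 4.123/0.379 = 30.5, against a maximum of 7.5 + 8.7 = 16.2.

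**Pain in 5.1.** The same bound, reading ± as SD:

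| Contrast | Printed p | Largest p if ± is SD | Implied correlation if ± is SE |
|---|---|---|---|
| A, day 1 vs day 0 | 0.014 | 4 × 10⁻⁷ | −0.03 |
| A, day 3 vs day 0 | 0.005 | 2 × 10⁻⁶ | 0.43 |
| Day 1, A vs B | 0.017 | 2 × 10⁻⁵ | 0.44 |
| Day 3, A vs B | 0.007 | 1 × 10⁻⁷ | 0.04 |

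Read as standard errors, the implied SDs (± × √17) are 2.23, 2.43 and 2.27 for A on days 0, 1 and 3, and 1.73 and 1.36 for B on days 1 and 3. The overall values cannot be standard errors. They would need SDs of 4.95 and 4.54, above the maxima that a 0–10 scale allows: √(m(10 − m) × 17/16) = 4.12 at m = 2.0 and 3.47 at m = 1.3.

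**The case against.** The impossibility of p = 0.86 and the conflict with the Abstract cannot be rebutted. The best counter-arguments concern attribution and weight.

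- **Attribution.** Reasoning from the F tests takes every other edema figure as correct, in a paragraph with at least one wrong entry, and 4.8 does not state which error term the LSD contrasts use. A one-digit slip, 126.1 for 123.1, would explain both the p-value and the wording of 5.3. It fails at the exact printed values. Within rounding, a day-7 mean from about 0.20 mm below to 0.13 mm above baseline survives, which includes 123.1, though only about 0.008% of random draws over the rounded inputs fit. This stands to the extent that the attribution is indicative and not proof. Table 4, which might settle it, is not shown.
- **Weight.** No between-group edema conclusion depends on this p-value, and the Abstract's own conclusion claims benefit for pain and trismus only. This stands and limits the consequence.
- **A separate issue.** Asking the Abstract to report the between-group null does not follow from the arithmetic. True, but it is needed whichever entry is wrong, and it concerns the same clause.
- **Pain.** Table 1 is not shown and might label the values as SE. The overall ± values could also be 95% CI half-widths (SDs about 2.33 and 2.14, correlation about 0.84). That is arithmetically possible, but SD is what 4.8 declares.

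**Conclusion.** The concern holds. With the printed means, SDs and 17 pairs, p cannot exceed 0.34 (0.36 with rounding) against a printed 0.86, and this bound assumes nothing about the correlation. Section 5.3's claim of resolution in Group A is unsupported as printed, and it contradicts the Abstract directly.

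The printed F tests point to the p-value or its contrast label as the error, and not to the mean. That inference assumes the other edema figures are right and that the contrasts are paired within group, so source data must decide. The between-group edema null is not overturned.

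The pain point is lesser and conditional: if the printed p-values are right, the daily ± values in 5.1 are not SDs, and standard errors fit. No pain test is overturned. Both points concern the text only, since Tables 1 and 4 are not shown.

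**What to change.** 1. Recompute the Group A day-7 mean, SD and baseline-versus-day-7 p from source data, check that the printed contrast is not day 2 versus day 7, and correct the wrong entry.
2. Make 5.3 and the Abstract agree. If 126.1 stands, remove the claim of resolution for Group A from 5.3. If the mean proves to be near baseline, remove the Abstract's restriction of regression to Group B.
3. In either case, state in the Abstract that edema did not differ between groups (treatment p = 0.48, interaction p = 0.23), and do not present within-group recovery as a group difference.
4. Check the five daily pain ± values against source data. Then print true SDs in 5.1 or label the values SE, and make 4.8 match.

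The cost is one edema contrast and five ± values to check, one clause to change, one sentence to add and one label to correct. No new data or model is needed.
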